9.2 Sample Size and Randomization

The trial size was determined based on hypothesized intervention effects on ACQ score, the primary outcome. We will recruit 254 individuals, but base power calculations on n=216 (108 per arm) anticipating $\leq 15\%$ loss to follow-up. With one baseline measure and 3 follow-up measures at 6, 12 and 18 months, the trial can detect an intervention effect of 0.25 ACQ score improvement using ANCOVA (or linear mixed models) method at 5% significance level and at least 80% power. This treatment effect is consistent with recent reported drug-trials for asthma control. Based on literature, for sample size estimation we assumed the mean (SD) of ACQ scores for the MBSR and HLC groups are 1.24 (0.66) and 1.49 (0.66) averaged over the three follow-up time points, respectively, and a serial correlation of 0.45 within patients. We expect to recruit patients from 12 physicians at each site, with on average each physician contributing 9 patients. Because within physician correlation has not been reported in literature and our small-sized pilot study does not allow an accurate estimation, we conservatively assumed a modest within physician correlation of 0.05. The sample size was estimated using Stata MP 12.

Our sample size estimation and power analysis are conservative and the treatment effect is chosen for other important reasons: a) to preserve the possibility of addressing treatment heterogeneity by select patient and physician characteristics (e.g. differential effects between male and female participants, ethnicity); we plan to conduct subgroup analysis and examine how treatment effects may differ. Such analysis will be very important when refining the treatment protocols and for dissemination if proved effective; b) other than the primary outcome, we are also interested in other primary/secondary outcomes described below and powered the trial to detect meaningful changes in these outcomes as well. The sample size is determined to allow us to achieve all these analytic goals, not just for the primary outcome.

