9.3 Definition of Populations

We will follow the intent-to-treat principle in the primary analysis. Study arm status of patients will be coded as randomized at enrollment, and the data will also be analyzed per protocol (versus actual interventions received). We will avoid potential switch of patients between arms. We anticipate the potential switch of study arms per patient is minimal to know. For missing data (e.g., missing visits or dropouts prior study completion), we propose to use multiple imputation methods that have become the standard approach in clinical trial studies and we routinely apply using Stata MP 13 (Stata Corp., College Station, TX).

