To compare the cost-effectiveness in asthma control and management between the comparator arms we will compute per-person incremental total cost per defined measure of additional clinical benefit. More specifically, total costs will include direct and indirect costs of intervention, and per-person overall healthcare/hospital care costs over the entire follow-up period to study completion. Key clinical endpoints will include prevention of exacerbations, unscheduled acute care office visits, and emergency room visits, as well as additional quality of life achieved. We will use general linear models to analyze the associations of the person-level intervention cost with ACQ scores, and use the model to predict per-arm required intervention effects. Secondly, we will use linear models to analyze the associations of person-level intervention cost with total healthcare/hospital care cost, and examine whether increases in intervention cost are correlated with lower average healthcare/hospital care cost. This "return-on-investment" analysis will provide information on monetary savings on care cost per dollar of MBSR intervention. Following these steps, we will apply log-linear models to analyzing the intervention-to-care cost ratios, and examine whether they differ by MBSR/HLC status, and other patient/physician factors.

Missing data: For most longitudinal trial studies, missing data and dropouts are unavoidable. To account for potentially differential/informative dropouts, we will apply inverse probability weighting methods that [name] developed for clinical trial studies with [name] and associates.^{104 #2421, 105} This method first estimates the probability of dropout/lost-to-follow-up of a participant based on his/her sociodemographic and health profiles, and uses the estimated probabilities as weights in the regression analysis. This method effectively removes

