potential bias associated with differential lost to follow-up (e.g., unequal rate of lost to follow-up by patient attributes or by intervention conditions) while following the intent-to-treat principle. In addition, this method can be modified to handle potentially non-random missingness, such as dropouts due to poorer outcomes. For example, whether a participant drops out at time point 3 may depend on his/her outcomes at time point 2. The model can be adapted to handle outcome dependent missingness. For missing data on covariates, we propose to use multiple imputation methods that have become the standard approach in clinical trial studies and we routinely apply using Stata MP 13 (Stata Corp., College Station, TX).

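### Section 9.6 names inverse probability weighting, but the weight it describes (the dropout probability) is not the weight that method uses for a completer, 1/(1−p)

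*Combined protocol and SAP*

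**What the plan says.** The missing-data paragraph of section 9.6 opens with the method: "we will apply inverse probability weighting methods that" were developed by a team member for clinical trials. Two earlier worksite trials are cited. The procedure is then described in two steps. First: "This method first estimates the probability of dropout/lost-to-follow-up of a participant based on his/her sociodemographic and health profiles". Second, the method "uses the estimated probabilities as weights in the regression analysis". The section says that this effectively removes "potential bias associated with differential lost to follow-up", including loss that differs by intervention condition, and that the model can be adapted when dropout depends on earlier outcomes. Multiple imputation is reserved there for missing covariates.

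Section 9.3, in the paragraph on the intent-to-treat analysis, gives a different rule: "For missing data (e.g., missing visits or dropouts prior study completion), we propose to use multiple imputation methods".

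The only probability that 9.6 defines is the probability of dropping out. Neither the probability of remaining under observation nor the step of inverting it is stated anywhere in the documents.

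**The concern.** Weighting for dropout works by letting each observed participant represent similar participants who were lost. A completer whose estimated dropout probability is p should count 1/(1−p) times. The text gives an analyst p as the weight. An analyst who notices the word inverse in the method's name and inverts the probability that was defined would use 1/p. Weighting by p gives far too much influence to completers who resemble dropouts. Weighting by 1/p gives them too little. Either choice shifts the analysed population away from the randomised one, costs precision, and can bias the arm difference, which the weighting is meant to protect.

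**Working it through.** **Inputs from the documents.** Section 9.2: 254 recruited, 216 analysed (108 per arm), at most 15% loss, 0.25 ACQ points to be detected "at 5% significance level and at least 80% power", SD 0.66, serial correlation 0.45, physician correlation 0.05 with 9 patients per physician. Section 6.2.2: 85% retention expected at 18 months.

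**Assumed, because the documents are silent.** The spread of p around its 15% mean; the ACQ gap between risk strata; a two-sided test.

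**The plan's own figures.** 216/0.85 = 254.1, which agrees with 254. A simple two-mean comparison at 108 per arm gives 79.5% power. Averaging three follow-ups, with variance factor (1 + 2×0.45)/3 and design effect 1 + 8×0.05 = 1.4, gives 84.0%. The sample size is consistent with its stated inputs and does not depend on the weights. The plan gives no figure for the weights themselves.

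**Weight ratios.** For p = 0.05, 0.15 and 0.30:
- weight p: 1 : 3 : 6
- weight 1/p: 6 : 2 : 1
- weight 1/(1−p): 1.053, 1.176, 1.429, that is 1 : 1.12 : 1.36

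**Effective sample.** Kish formula among completers, (Σw)²/Σw², scaled to 216, with two equal strata. Worked case, 5%/25%: completer fractions are 0.5×0.95 = 0.475 and 0.5×0.75 = 0.375, total 0.85.
- w = p: Σw = 0.475×0.05 + 0.375×0.25 = 0.1175; Σw² = 0.475×0.0025 + 0.375×0.0625 = 0.024625. Effective N = 216 × 0.1175²/(0.85×0.024625) = 142.5.
- w = 1/(1−p): Σw = 1; Σw² = 0.475/0.9025 + 0.375/0.5625 = 1.1930. Effective N = 216 × 1/(0.85×1.1930) = 213.0.

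| Dropout in the two strata | w = p | w = 1/(1−p) |
|---|---|---|
| 15% / 15% | 216 | 216 |
| 12% / 18% | 207.6 | 215.7 |
| 10% / 20% | 193.7 | 215.3 |
| 5% / 25% | 142.5 | 213.0 |

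A logistic dropout model averaging 15%, with slope 0.25, 0.5 or 1.0 per SD of the predictor, gives 207, 184 and 132 for w = p, against 216, 215 and 210 for 1/(1−p).

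**Population represented.** With 5%/25%, the higher-risk half of those randomised carries 0.375/0.85 = 44% of the weight unweighted, 50% under 1/(1−p), and 0.09375/0.1175 = 80% under p.

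**Bias in the arm difference (illustration).** True effect −0.25 in both strata; strata differ by 0.5 ACQ points; dropout 5%/25% in the MBSR arm and 10%/20% in the HLC arm. The estimate is −0.25 + 0.5 × (high-risk weight share in MBSR − share in HLC).
- Unweighted: shares 0.4412 and 0.4706; estimate −0.265.
- 1/(1−p): shares 0.5 and 0.5; estimate −0.250.
- p: shares 0.798 and 0.080/0.125 = 0.640; estimate −0.171.
- 1/p: shares 1.5/11 = 0.136 and 2/6.5 = 0.308; estimate −0.25 − 0.5×0.171 = −0.336.

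If the dropout pattern is the same in both arms, the shares are equal, the gap cancels, and a constant treatment effect is recovered under any of the weights. In that case only precision and the population represented are affected.

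**The case against.** The strongest reply is that the sentence is shorthand. The method is correctly named immediately before it and earlier trials are cited as applications, so a statistician who knows the technique would probably compute the standard weight. This stands in part: the documents do not show that anyone intends to weight by p, and a reader should not infer that they do. It does not remove the defect. The name and the described steps disagree, the probability defined is the wrong one to invert, and no other section supplies the right one.

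Two stronger readings are also tempting.
- A reader might infer that the primary intent-to-treat estimate would be dominated by a few completers at high risk of dropout. The documents do not support this. Section 9.3 assigns multiple imputation to dropouts, so it is not settled that these weights govern the primary estimate. In the 5%/25% example the excess weight falls on half of the randomised sample, not on a few people.
- A reader might infer a definite loss of power below the planned 80%. Any such figure needs a spread of dropout risk that the plan does not state, and the loss is nil if risk is constant.

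It is also fair that 9.6 already foresees loss that differs by arm and dropout that depends on earlier outcomes. Naming those predictors therefore completes the plan and does not correct it.

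**Conclusion.** The point holds as a contradiction between the named method and the described weight. Neither p nor 1/p is the inverse probability weight for a completer, and the claim that bias is removed is true of neither. Confidence is high about the wording and limited about what would actually be computed.

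The consequence is conditional. With average dropout of 15%, weighting by p costs nothing if risk is uniform, about 4% of the effective sample for 12%/18% strata, and about 34% for 5%/25%. When dropout patterns differ by arm and risk is related to ACQ, weighting by p can distort the difference more than leaving the data unweighted: an error of 0.079 against 0.015 in the illustration, on a target effect of 0.25. These sizes rest on assumed strata and an assumed ACQ gap. They show direction and order of magnitude and do not predict this trial's result. The planned 254 recruited and 216 analysed are unaffected.

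**What to change.** In 9.6, replace the description of the weights with an explicit definition: each observed participant is weighted by the inverse of the estimated probability of remaining under observation, 1/(1−p), where p is the estimated dropout probability. State that the dropout model includes arm, baseline ACQ and the most recent observed ACQ alongside the sociodemographic and health variables already mentioned, and that standard errors are robust. The first sentence corrects the error; the rest completes the specification.

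Then reconcile 9.3 with 9.6: say whether weighting or multiple imputation handles missing ACQ outcomes in the primary intent-to-treat analysis, and make the other a sensitivity analysis or remove it.

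The cost is a sentence or two in 9.6 and one in 9.3. The ACQ is already scheduled at baseline and at each follow-up, so there is no change to data collection or sample size.

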10. DATA COLLECTION AND QUALITY ASSURANCE

10.1 Data Collection Forms

Data will be collected by the study Research Assistant on both pre-tested and validated hard copy forms found to be acceptable by the type of individuals who will participate in this project and via a secure online process for patient monitoring.

We will use the Research Electronic Data Capture (RedCap) database system to manage data for this trial. REDCap originated out of the Vanderbilt Institute for Clinical and Translational Research, and has been used by numerous NIH-funded RCTs (<http://www.projectredcap.org/>). It has been proved to be cost-effective, efficient and robust, and very good peer-to-peer support. UMass Medical School is a member of the REDCap consortium (which has over 1,000 institutional members), and has dedicated IT staff to support the operation.

RedCap is a secure web application for building and managing online surveys and databases. Using RedCap's stream-lined process for rapidly developing projects, project staff can create and design projects using 1) the online method from your web browser using the Online Designer; and/or 2) the offline method by constructing a 'data dictionary' template file in Microsoft Excel, which can be later uploaded into REDCap. Both surveys and databases (or a mixture of the two) can be built using these methods. REDCap provides audit trails for tracking data manipulation and user activity, as well as automated export procedures for seamless data downloads to Excel, PDF, and common statistical packages (SPSS, SAS, Stata, R). Also included are a built-in project calendar, a scheduling module, ad hoc reporting tools, and advanced features, such as branching logic, file uploading, and calculated fields.

In this project, the RedCap database system will be used for both data entry/user interface and the tracking system. RedCap is fully HIPPA compliant. Regular data verification and checks for protocol compliance with data collection will occur via blinded double data entry, checks of ranges during the data entry process, and checks for values outside of allowable bounds.

The participating clinical sites are responsible for data collection, and securely transmit the data collection forms to the data management/statistical center for data entry and cleaning. The clinical sites are responsible for answering inquiries from the data center regarding data quality issues (such as missing items, erroneous answers). After data entry and quality control is complete, the data center is responsible for transporting the data collection forms to the project manager at UMMS to store and safe-guard the data forms in a safe location.

The data center at HSGL is responsible for producing periodic reports for monitoring the study progress, and generating data reports to be submitted to DSMB and NCCAM.

The Human Subjects Committee (HSC) at UMMS is a fully authorized Institutional Review Board (IRB) that provides oversight to research conducted at the medical school. It functions in compliance with the congressional statutes governing human research detailed in the University of Massachusetts Medical School “Assurance of Compliance with Health and Human Services (HHS) Regulations for Protection of Human Research Subjects”. This committee will be providing oversight to the current study.

10.3.3. Metrics: All paper-based data outcome points (primary and non-primary) and data that has been directly entered in the database will be subject to verification by a data analyst under the supervision of the study data manager. The data analyst will correct all errors during the verification process. On a monthly basis, the study data manager will perform an additional data audit of all outcome points. This audit must have an error rate less than 1%. If the error rate exceeds 1% during this secondary verification process, all data will be re-entered, the original computer files discarded, and the newly re-entered data audited. This process will continue until the audit no longer exceeds the maximum allowable error rate. All errors encountered during the secondary audit process will be documented by the study data manager.

10.3.4. Protocol Deviations: All protocol deviations/violations and unanticipated problems will be logged on an ongoing basis throughout the study and this will be reported to the data safety monitor.

10.3.5. Monitoring: Site monitors designated by NCCAM will visit UMMS to assure protocol compliance and data quality including review of records, consents and study files. Where travel restrictions or personal distance requirements due to the COVID-19 pandemic restrict on-site visits, staff at each site will request approval from their IRB to allow remote access to NCCIH monitors to review of records, consents and study files on-line. All final protocol revisions and NCCIH PO approvals will be provided to the Miriam site in real time. Implementation will be confirmed verbally and via email by Miriam staff, and visually during UMMS site visits to Miriam via review of their records conducted every 6 months using a structured Site Visit Checklist. This Site Visit Checklist includes review of the protocol, informed consent forms, case report forms, eCRFs, source documents, participant folders, tour of the facilities, HIPPA requirements, regulations, study personnel, safety reporting, and regulatory binder.

11. PARTICIPANT RIGHTS AND CONFIDENTIALITY

11.1. Institutional Review Board (IRB) Review

This protocol and the informed consent document and any subsequent modifications will be reviewed and approved by both the UMMS IRB and the Miriam Hospital IRB. The University of Massachusetts Medical School/UMMC will be the coordinating institution, receive reporting of all AEs, and will be responsible for oversight of the study.

11.2. Informed Consent Forms

Consent will be obtained at two time points during the study: 1) at the initial phone screening, and 2) at the orientation session.

1) As in our prior studies, a HIPAA waiver authorization will be requested from our respective Institutional Review Boards prior to obtaining the list of apparently eligible patients. Interested patients will be called by the Research Assistant (RA) at each site. The RA will briefly describe the study and its requirements and it will be explained that the patient’s overall care at their hospital will in no way be affected by whether or not the patient participates in the study. The RA will then enquire if the patient is still interested. If the caller is interested the RA will explain the need to collect some information from the patient to determine whether they are eligible to participate and request verbal permission to proceed. Upon obtaining verbal consent the RA will complete the phone screen which will include questions related to eligibility. A script and screening form will be used to standardize this phase of enrollment.

If the patient is eligible, the RA will schedule an in-person consent/baseline session with that individual.

2) Eligible persons will attend a consent/baseline session at the study offices at that site during which the RA will explain the study goals and procedures. This will be designed to familiarize potential participants with the study, what to expect and what is expected of their participation, both in the interventions and research assessment aspects of the study. Individuals who wish to enroll will provide written consent using an IRB-approved and dated consent form. In addition to describing the study and the participant’s involvement in detail, the consent form also emphasizes that participation is voluntary, that consent may be withdrawn at any time, and that participants may withdraw from the study verbally or in writing by contacting the study RA and/or

the contact Principal Investigator. Contact information for the RA and the PI, as well as the IRB (for complaints) is provided in the consent form. Copies of the signed consent form are retained by the study and the participant. Participants are given ample opportunity to ask questions before providing consent. [name] the Project Director will supervise the RA to maintain consistent delivery of the orientation sessions. Study eligibility criteria include being aged 18 and over, and being able to read and understand English, and complete informed consent process and study data collection procedures.

After providing written consent they will complete the baseline assessments and be randomly assigned to one of the two study arms by the data manager at UMMS. Randomization will be stratified by site and asthma severity with each stratum in randomly allocated block sizes of two using the ralloc program in Stata.^{82, 83} The randomizations will be conducted for each cohort to ensure that the seasonality and temporal effects be adequately controlled by design.

11.3. Participant Confidentiality

Protection of Subject Privacy: Participant confidentiality will be maintained by the use of a number of strategies. The study phone will be located in a private, locked office and be answered by the trained RA who has been trained and certified in the protection of human subjects in research trials and HIPPA requirements according to UMMS policies.

Since the interventions occur in a group setting that includes individuals not enrolled in the study it will be impossible to guarantee privacy of information that participants share in that group setting. However, at the beginning of each intervention class the instructor will emphasize the privacy of information shared in the group.

Database Protection: Data collected for eligibility screening will not contain any identifiers. These data will be entered into a secure database for later analysis of reasons for ineligibility for the study.

Each enrolled participant will be assigned a unique study identification number to maintain confidentiality. The only individual who will have access to these identifiers will be the Research Assistant responsible for data collection and [name], the Project Director. UMMS and Miriam Hospital personnel will not be privy to identifying information about the individual participants. Subsequent protection of study data will be assured by the use of locked filing cabinets separate from the cabinets used to collect identifiers (contact information) and password-protected computer data bases with access available only to the principal study personnel. Any data, forms, reports or other records that leave the site will be identified only by the study identification number to maintain confidentiality. Information will not be released without written permission of the participant, except as necessary for monitoring by IRB, the FDA, the NCCAM, and the OHRP. See section 10.3.2 for a description of the plan for data and safety monitoring of the research to ensure the safety of subjects.

